## **A Mobile Health Intervention to Achieve Appropriate Gestational Weight Gain in Overweight/Obese Women**

### **CLINICAL TRIAL PROTOCOL**

#### **Abbreviations:**

BMI:	body mass index
GWG:	Gestational weight gain
IOM:	Institute of Medicine
IRB:	Institutional Review Board
KPNC:	Kaiser Permanente Northern California
mHealth:	mobileHealth
PA:	physical activity
RCT:	randomized controlled trial

#### **OBJECTIVE:**

We conducted a cluster RCT of an mHealth intervention promoting appropriate GWG in pregnant patients with overweight or obesity in KPNC, an integrated healthcare system. Randomization was at the clinician level. The primary aim of this clinical trial is to evaluate whether an mHealth intervention designed to help pregnant patients with overweight or obesity and their clinicians manage GWG will improve GWG (Primary Outcome) in comparison to usual care.

#### **BACKGROUND:**

Sixty percent of pregnant patients in the United States are overweight or obese. Over half of pregnant patients with overweight or obesity exceed the IOM guidelines for GWG, which further increases their elevated risk of gestational diabetes, cesarean delivery, postpartum weight retention, severe obesity later in life, having a large-for-gestational-age infant and a child at risk of being overweight or obese. Thus, improving GWG among patients with overweight or obesity is a public health priority. Pregnancy is a unique window when women are in frequent contact with the health system and are motivated to make healthful changes out of concern for their baby, which presents an unparalleled opportunity to intervene on weight management. High-intensity behavior change interventions have significantly improved the percent of women meeting the IOM GWG guidelines. However, these interventions are too time-consuming for some patients. In addition, while patients view their clinicians as a persuasive, trusted source of behavior change advice, many clinicians lack experience and the tools to provide behavior change advice necessary to manage GWG. Interventions to manage GWG that support both patients' and clinicians' barriers, and can be implemented in the health system, could maximize their effectiveness and reach.

MHealth interventions offer a promising scalable solution to overcome patients' and clinicians' barriers to GWG management but have yielded mixed results. We propose that mHealth interventions must include key elements to impact weight. These include interactive technologies

such as “smart” wireless scales and wearable activity trackers that facilitate self-monitoring and real-time feedback. These elements have proven efficacious in weight management outside of pregnancy but were not previously included in mHealth GWG interventions. We also propose that tools and training for clinicians are essential.

### **STUDY DESIGN:**

This study conducted a cluster randomized trial to evaluate an mHealth intervention promoting appropriate GWG in an integrated healthcare system, with randomization at the clinician level. Consented patients received usual care or usual care plus mHealth intervention per their clinician’s randomization. The patient adaptive intervention provided personalized, automated feedback on GWG and physical activity using 1) a smartphone application, 2) a Wi-Fi scale and activity tracker; 3) weekly educational topics; and 4) step-wise support (added when GWG is >75th percentile of the GWG guidelines). Intervention clinicians received newsletters with motivational interviewing tips to facilitate discussing GWG.

### **STUDY POPULATION:**

#### a. NUMBER OF SUBJECTS

58 total clinicians

1,335 total patients

#### b. INCLUSION AND EXCLUSION CRITERIA

Inclusion Criteria:

- Age 21 years or older
- Pregnant
- Women receiving prenatal care at Kaiser Permanente San Francisco and Oakland and whose obstetric care clinicians consent to participate
- Pregravid BMI 25 to <40 (as determined from a measured pregravid weight in electronic medical record)
- Has access to a smartphone and Wi-Fi
- Provides informed consent to participate

Exclusion Criteria:

- Multiple births
- Planning to move out of the area during the study period
- Inability to speak, read, or understand English
- Placed on bed rest at time of enrollment
- > 15 weeks' gestation at enrollment.

**WAIVER OF INFORMED CONSENT and HIPPA PRIVACY RULE AUTHORIZATION:**

A waiver of informed consent and HIPPA Privacy Rule Authorization was granted from KPNC IRB (IRB of record for this study) for clinicians and patients in the intervention arm and in the usual care arm. The only known risk is disclosure of confidential information. Safeguards were be put in place to prevent the loss of privacy and to prevent breaches of confidentiality. This study represented no more than minimal risk participants.

**STUDY PROCEDURES:**

Eligible clinicians were randomized into (2) arms: 1) an intervention arm and 2) a usual care arm. Obstetric clinicians randomized to the intervention arm received quarterly newsletters containing study updates on recruitment and retention efforts plus quarterly intervention newsletters containing tips on how to use motivational interviewing techniques to discuss GWG with their pregnant patients. Obstetric clinicians randomized to the usual care arm received quarterly newsletters containing study updates on recruitment and retention efforts.

Pregnant patients receiving prenatal care from consented clinicians were eligible to participate in the trial. Eligible patients of consented clinicians in both arm were invited to complete a trial survey. Patients in both arms were informed they might be invited to an mHealth program. Within one week of completing the survey, patients receiving care from clinicians in the intervention condition were subsequently invited to join the adaptive mHealth intervention and invited to consent to sharing app, activity, and weight data with the study team.

**DATA ANALYSIS:**

All data analyses were intent-to-treat, including all randomized clinicians and patients. Analysis of treatment arm differences was by original treatment group assignment, regardless of adherence. Log binomial regression was used to estimate the population average mHealth intervention effect on meeting the IOM GWG guide lines with estimation via generalized estimating equations (GEE; marginal model), accounting for the within-clinician correlation among patients to obtain valid estimates of treatment effects and associated standard errors. The probability of appropriate total GWG was modeled as a function of treatment arm and covariates used in the randomization procedure: clinician age, patient race/ethnicity, and patient BMI. In addition, this a priori specified set of model covariates included patient age and parity in the regression models given their strong association with GWG.

Linear regression was used to provide point and interval estimates of the between-arm difference in mean rate of GWG. The approach to estimation of model parameters (GEE) and inclusion of model covariates was as specified above for the analysis of our primary binary outcome. Linear regression with GEE was chosen rather than linear mixed effects regression for estimation of population average intervention effects given freedom from

distribution assumptions on cluster random effects, and to parallel the analyses of our binary outcome.

The approach to the analyses of trimester-specific GWG (kg/week) paralleled that described above for the total rate of GWG. Linear mixed effects models were used in analyses of the intervention in relation to GWG trajectory, accounting for the within-person correlation among repeated measurements (not necessarily equal numbers per subject) and within-clinician correlation between patients, to obtain valid estimates of treatment effects and associated standard errors. We used latent trajectory class modeling to identify and categorize patients with respect to patterns of GWG during pregnancy. Group-based trajectory analysis, an application of finite mixture modeling, is designed to identify clusters of individuals with similar patterns of change over time. Examination of the intervention in relation to pattern of change category utilized multinomial logistic regression with estimation via GEE to account for nesting within clinician. The approach to the analyses of postpartum weight retention at 6 weeks, change in moderate to vigorous physical activity (12 weeks to 33 weeks; MET hrs/week), overall diet quality at 12 weeks (Healthy Eating Index-2015), and birthweight (all continuous), and proportion of infants with appropriate size for gestational age (binary) paralleled that described for the primary outcomes or rate of GWG and meeting the IOM GWG guidelines. The approach to the analyses of the intervention in relation to 12-month infant growth (BMI Z-score) trajectory paralleled that described for analyses of GWG trajectory.

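### The guideline outcome pools gain above and below the range, and no listed analysis reports either bound, so a fall in excess gain cannot be told from a rise in inadequate gain

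*Combined protocol and SAP*

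**What the plan says.** The Data Analysis section defines the binary outcome: "Log binomial regression was used to estimate the population average mHealth intervention effect on meeting the IOM GWG guide lines". The model is then described: "The probability of appropriate total GWG was modeled as a function of treatment arm" and a fixed set of covariates, fitted by GEE with clustering by clinician. A continuous outcome is analysed beside it: "Linear regression was used to provide point and interval estimates of the between-arm difference in mean rate of GWG". Later in the same section both are referred to as primary outcomes.

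The other weight-gain analyses listed are trimester-specific rate, a mixed-model trajectory, and data-driven trajectory classes compared by multinomial GEE. For the infant, the plan lists continuous birthweight and the "proportion of infants with appropriate size for gestational age (binary").

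Three other statements bear on direction. Background: "Over half of pregnant patients with overweight or obesity exceed the IOM guidelines for GWG". Study Design: "The patient adaptive intervention provided personalized, automated feedback on GWG and physical activity", and, as one of four components, "step-wise support (added when GWG is >75th percentile of the GWG guidelines"). The waiver section: "The only known risk is disclosure of confidential information".

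No part of the supplied text lists gain above the range, or gain below it, as an outcome in its own right.

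**The concern.** A woman can miss the guideline in two opposite ways, and the binary outcome records both as the same failure. The harms listed in the Background are harms of excess gain, and the only escalation step described is triggered by high gain, so any effect is likely to be downward. A woman who moves from above the range to within it adds a success. A woman who moves from within the range to below it removes one. The binary outcome shows only the net result.

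Mean rate of gain does not fill the gap, because less excess and more inadequate gain both lower it. The two primary results could therefore differ, with a lower mean rate and little change in attainment, and no listed analysis would explain why. What is at stake is whether the trial can say that it reduced excess gain, and whether it can show that it did not increase inadequate gain. The waiver section names no risk of the second kind, and no listed outcome would check for it at the guideline's lower bound.

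Infant size is affected in the same way. The Background names large-for-gestational-age infants as a harm, but the binary outcome merges large with small. Mean birthweight has a direction but does not count either group.

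**Working it through.** The plan gives no power, effect size, SD, intracluster correlation (ICC) or rate of below-range gain, so there is no stated figure to reproduce. Everything below is illustration.

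**Inputs from the documents:** 1,335 patients, 58 clinicians, and more than half above the range in the background population.

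**Assumed:** normally distributed total gain; the SD, range width, share above and shift given at each step; 1:1 allocation; two-sided alpha 0.05; ICC 0 to 0.03.

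**Step 1. Uniform downward shift.** Take SD 6 kg, width 4 kg, 55% above in usual care and a shift of 1.5 kg. Measure gain from the usual-care mean. The upper bound is U = −0.126 × 6 = −0.754 kg, and the lower bound is L = −0.754 − 4 = −4.754 kg. With Φ the standard normal distribution function:

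| Category | Usual care | After shift |
|---|---|---|
| Above | 1 − Φ(−0.126) = 55.0% | 1 − Φ((−0.754 + 1.5)/6) = 1 − Φ(0.124) = 45.1% |
| Below | Φ(−4.754/6) = Φ(−0.792) = 21.4% | Φ((−4.754 + 1.5)/6) = Φ(−0.542) = 29.4% |
| Within | 23.6% | 25.6% |

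The risk ratio for within is 25.6/23.6 = 1.08. Over SD 5 to 7 kg, width 4 to 4.5 kg, 50% to 60% above and a shift of 1 to 1.5 kg, above falls 5.6 to 11.9 points, below rises 4.1 to 9.7, and within rises only 0.7 to 4.6.

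**Step 2. Shift only the women with high gain.** Keep the values of Step 1, but move only women more than three quarters of the way up the range (an assumed reading of the trigger). That threshold lies 3 kg above L, so a 1.5 kg shift takes nobody below L. Above falls to 45.1% as before, below stays at 21.4%, and within becomes 100 − 45.1 − 21.4 = 33.5%. The rise is 9.9 points and the risk ratio is 1.42. There is no masking.

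**Step 3. What this does to power.** Mean cluster size is 1,335/58 = 23.0. At ICC 0.01 the design effect is 1 + (23.0 − 1) × 0.01 = 1.22, so the effective size per arm is 667.5/1.22 = 547. Power uses the normal approximation for two proportions or two means.

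Take usual care as 55% above, 30% within and 15% below, and shift everyone down by 0.2 SD:

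- above 55% to 47.0%, power 0.75
- below 15% to 20.1%, power 0.61
- within 30% to 32.8%, power 0.17
- mean rate: Φ(0.2 × √(547/2) − 1.96) = Φ(1.35) = 0.91

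With ICC 0 to 0.03, 52% to 65% above and 10% to 25% below in usual care, power for the same shift is 0.06 to 0.33 for within, 0.60 to 0.83 for above and 0.81 to 0.95 for mean rate.

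Now fix the fall in excess gain at 55% to 45% (power 0.91 if analysed alone, ICC 0.01) and vary the rise in below-range gain from 15%:

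| Rise in below-range gain | Within | Power for within |
|---|---|---|
| 0 points | 30% to 40% | 0.94 |
| 3 points | 30% to 37% | 0.69 |
| 5 points | 30% to 35% | 0.42 |
| 8 points | 30% to 32% | 0.11 |
| 10 points | no net change | chance level |

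Masking is thus governed by one quantity, the rise in below-range gain, and the plan does not report that quantity.

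**The case against.** The case for leaving the plan alone is substantial.

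- **The outcome fits the aim.** The Objective speaks of appropriate gain, and the Background judges earlier interventions by guideline attainment. Counting a move below the range as a failure is itself a safeguard that an excess-only outcome would lack. This stands, and it is why the binary primary should be kept.
- **Masking is conditional.** Step 2 shows that it vanishes if only high gain is affected, and nothing in the documents shows that under-gain would rise. This stands. However, baseline feedback on gain goes to all intervention patients and is not described as limited to high gain, so a wider shift is not ruled out either.
- **A second primary outcome would detect the shift.** This stands. A reader might infer that a real effect could leave the whole trial looking null. The documents do not support that, since the offset affects the binary outcome only.
- **A lower mean with flat attainment would hint at movement at both ends.** This stands only in part. The same pattern arises if women above the range gain less but stay above it.
- **Trajectory classes, trimester rates and birthweight bear on low gain.** They do, so it would be too strong to say that inadequate gain leaves no trace in the reported results. None is tied to the guideline's bounds, however.

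A reader might also infer that the plan treats any fall in mean rate as an improvement. It does not. It promises point and interval estimates of a difference and gives neither direction a label.

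**Conclusion.** The gap is real and limited. The binary primary is a reasonable choice and is not an error. What is missing is any analysis, in the supplied text, that reports gain above or below the range separately. Without one, the trial cannot show directly whether excess gain fell or inadequate gain rose.

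The size depends on how the intervention acts. Under the assumed uniform 1.5 kg shift, a fall of about 10 points in excess gain appears as a rise of 2 points in attainment. If only high gain is affected, the same fall appears almost in full. The SD, range width, baseline split, ICC, alpha and allocation ratio are all assumptions, so these figures show a mechanism and do not predict the result. The conclusion that neither bound is reported does not depend on them.

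**What to change.** Keep the binary primary as it is. Add below/within/above by arm as a secondary analysis. Use either the multinomial GEE approach already planned for trajectory class, or two log-binomial GEE models, one for above and one for below, with the same covariates and clinician clustering as the primary. Give risk ratios with confidence intervals for each bound when the separate models are used, and report below-range gain as a safety outcome. Report infant size as small/appropriate/large in the same way.

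The plan is written in the past tense. If the data have already been analysed, label these analyses as added, not as pre-specified.

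The cost is a few lines of text and a few more secondary estimates. No new gain data are needed, because classifying a woman as within range already uses both bounds. The downside is a less favourable reading if below-range gain turns out to have risen.

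### Medical center is missing from the stated adjustment set of the primary and parallel models, at a small to moderate cost in precision

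*Combined protocol and SAP*

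**What the plan says.** The eligibility criteria restrict enrollment to "Women receiving prenatal care at Kaiser Permanente San Francisco and Oakland", which makes two centers. The study population section gives "58 total clinicians" and "1,335 total patients". Study Procedures says that "Eligible clinicians were randomized into (2) arms", and no stratification by center is described.

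Under Data Analysis, the primary log-binomial model contains treatment arm and "covariates used in the randomization procedure: clinician age, patient race/ethnicity, and patient BMI". It then states that "this a priori specified set of model covariates included patient age and parity". Estimation is by GEE, "accounting for the within-clinician correlation among patients". The linear model for rate of gestational weight gain (GWG) takes the same covariates. Several other outcomes are said to be analyzed in the same way: trimester-specific gain, postpartum weight retention, physical activity, diet quality, birthweight and size for gestational age.

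The GWG trajectory mixed model, the infant growth model that follows it, and the multinomial model for trajectory class name their correlation levels but give no covariate list. Center appears nowhere as a randomization factor, covariate, clustering level or sensitivity analysis.

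**The concern.** Center sits above the randomized unit and precedes randomization. Two centers can differ in patient mix and in how weight gain is discussed and managed. If they differ in the proportion meeting the guideline, that difference is part of the between-clinician variation, and a model without center leaves it there.

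This has one of two consequences, depending on how randomization was done:

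- **Center not balanced.** With only 58 clusters, the arms can differ noticeably in center mix by chance. The treatment estimate then carries part of the center difference.
- **Center balanced but not described.** The estimate is protected, but the clinician-level standard error still includes between-center variation and is too large.

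Both cases favor a center term. At stake is the width of the confidence interval and how well this one realized allocation is handled.

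**Working it through.** The text available contains no sample-size calculation, ICC or effect size, so there is no planned figure to reproduce. The calculation below shows scale only. It is on the risk-difference scale, for simplicity; the plan's model is log-binomial.

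**Inputs from the documents:** K = 58 clinicians and N = 1,335 patients, so m = 1,335/58 = 23.0 patients per clinician; two centers.

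**Assumptions:** 29 clinicians per arm (the ratio is not stated); equal cluster sizes; equal centers, with smaller-center sizes of 20 and 15 as checks; p = 30-40% meeting the guideline (the Background says only that over half exceed it); ICC 0.01-0.05, meaning the correlation *remaining after center is removed*; a residual center difference D of 5 or 10 points.

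**Step 1: chance imbalance.** With q the share of clinicians in one center and no balancing, the between-arm difference in center share has SD = sqrt(4q(1-q)/(K-1)).

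- 29/29 clinicians: sqrt(1/57) = 0.132
- 20/38: 0.126
- 15/43: 0.116

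With equal centers, the chance of a difference of at least 10 points (3/29 or more) is 60%, and of at least 24 points (7/29) is 11%.

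**Step 2: standard error with center in the model.** SE = sqrt(4p(1-p)[1+(m-1)ICC]/N).

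- ICC 0.01: 2.77 points (p = 0.30) to 2.96 (p = 0.40)
- ICC 0.03: 3.23 to 3.46
- ICC 0.05: 3.64 to 3.89

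**Step 3: standard error without center.** SE' = sqrt(SE² + (D × 0.132)²). The added error has SD 0.66 points for D = 5 and 1.32 for D = 10. At ICC 0.01 and D = 10, the standard error goes from 2.77 to 3.07 (p = 0.30) and from 2.96 to 3.24 (p = 0.40).

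| Residual ICC | SE inflation, D = 5 | SE inflation, D = 10 |
|---|---|---|
| 0.01 | 2.5-2.8% | 9.5-10.8% |
| 0.03 | 1.8-2.1% | 7.1-8.1% |
| 0.05 | 1.4-1.6% | 5.6-6.4% |

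With a 15/43 split of centers, the ranges over the same ICCs are 1.1-2.2% and 4.4-8.4%.

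**Step 4: a single allocation.** A 20-point imbalance in center share would move the estimate by 0.20 × 5 = 1.0 point, or 0.20 × 10 = 2.0 points. The standard errors in Step 2 are 2.8 to 3.9 points.

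**Step 5: power, for illustration.** For an assumed effect of 30% versus 40%, two-sided 0.05 and residual ICC 0.03, power is about 0.85 with center in the model. Without it, power is about 0.84 (D = 5) or 0.80 (D = 10).

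Chance imbalance and standard-error inflation are two views of the same loss and should not be added together.

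**The case against.** The case against has four parts.

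- **No rule of the plan is broken.** The model adjusts for every factor said to have been used in randomization, and adds two strong predictors. A further baseline covariate is discretionary, and nothing in the documents shows that center predicts the outcome. This stands as far as it goes. But adjusting for a factor fixed before randomization does not require prior proof of its effect.
- **Inference is already valid.** A reader might infer that leaving center out biases the treatment effect or invalidates its standard error. The documents do not support that. Randomization keeps the estimate unbiased on average, and clustering by clinician carries unmodelled center variation into the standard error.
- **The size rests on assumption.** This stands. The center difference, the ICC, the proportion meeting the guideline and the clinician split are all assumed. The ICC must be read as residual: a 10-point gap between equal centers alone contributes D²/4 ÷ p(1-p) = 0.0025/0.24 to 0.0025/0.21, or 0.010-0.012. If 0.01 were the total clinician ICC, that gap would use all of it and a 15-point gap would be impossible. Race/ethnicity, BMI and the other covariates may also absorb part of any gap. If they absorbed half of a 10-point gap, the 5-point column would apply.
- **The analysis is described as done.** The text is in the past tense and calls the covariate set a priori, so a covariate added now would not be pre-specified. This stands and shapes the fix.

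None of this removes the precision gain from including center.

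**Conclusion.** The point holds as a minor, low-cost improvement. Center is absent from the covariate set of the primary, rate-of-GWG and parallel models. The consequence is lost precision and exposure to chance center imbalance, or conservative standard errors if center was balanced in a way not described.

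Under the stated assumptions, standard-error inflation is about 1-3% for a 5-point residual center difference and about 6-11% for 10 points. It is less if the existing covariates absorb part of the difference. So the effect is slight for modest differences and worth having only near 10 points or more.

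Two broader readings go beyond the text. A reader might conclude that center is left out of every model, but the trajectory and multinomial models give no covariate list, so there the plan is only silent. A reader might also assume that center is recorded for every clinician. That is a reasonable inference from the eligibility criterion, but it is not stated.

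**What to change.** Add one fixed medical center indicator to the covariate set of the primary model, the rate-of-GWG model and the models that follow them. State the covariates of the trajectory and multinomial models, including whether center is among them. Say whether center played any part in the randomization.

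If the analyses are already complete, leave the primary model as it is. Report the center-adjusted result as a sensitivity analysis labelled not pre-specified. In either case, tabulate clinicians and patients by center and arm, so that a reader can see the realized imbalance.

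The cost is one cluster-level degree of freedom out of 58, and confirmation that each clinician belongs to a single center. If some work at both, the indicator should follow the patient's place of care.

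### Should the first trimester be set apart in the trimester-specific weight-gain analysis, and early gain added to the rate model?

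*Combined protocol and SAP*

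**What the plan says.** Three parts of the combined protocol and SAP bear on this.

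- **Timing of the app.** Under inclusion and exclusion criteria, patients are excluded if "> 15 weeks' gestation at enrollment"; no lower limit is given. STUDY PROCEDURES puts the app offer after the survey: "Within one week of completing the survey, patients receiving care from clinicians in the intervention condition were subsequently invited to join".
- **Clinician component.** STUDY DESIGN says "Intervention clinicians received newsletters with motivational interviewing tips to facilitate discussing GWG". STUDY PROCEDURES makes these quarterly and does not tie them to when a patient enrols.
- **Analysis.** DATA ANALYSIS handles the trimesters in one sentence: "The approach to the analyses of trimester-specific GWG (kg/week) paralleled that described above for the total rate of GWG". For the rate model, the "inclusion of model covariates was as specified above for the analysis of our primary binary outcome". That set holds the covariates used in randomization (clinician age, patient race/ethnicity, patient BMI), and "this a priori specified set of model covariates included patient age and parity in the regression models given their strong association with GWG". Weight gained before enrolment is not in it. The same section also plans mixed models of the weight-gain trajectory from repeated measurements.

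**The concern.** A patient who enrols at 10 or 12 weeks cannot have used the app for most of her first trimester. If the first-trimester rate is compared between arms like the other two, a null result could be read as the app failing early, and a difference as the app working early. For many permitted enrolment weeks the app could have contributed little or nothing to that period.

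The second strand concerns the rate model. Gain before the app starts is part of the outcome's variability if the rate is measured from the pregravid weight. Leaving it in the residual costs some precision. It also leaves no check on early differences between arms, which are possible because patients joined after their clinicians were randomized. The plan's own reason for adding age and parity, that they predict weight gain, would seem to apply to early gain too.

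**Working it through.** The documents give no power, effect size, standard deviation (SD) or intraclass correlation (ICC), so there is no design figure to reproduce. From the documents: enrolment up to week 15, invitation 0-1 week after the survey, 58 clinicians and 1,335 patients. Assumed: the survey marks enrolment, and the first trimester lasts T = 13 or 14 weeks.

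**1. Share of the first trimester before app invitation**

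Share = min(1, (enrolment week + lag)/T). The lowest value uses lag 0 and T = 14; the highest uses lag 1 and T = 13.

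| Enrolment week | Lowest | Highest | Visible part of a constant weekly app effect |
|---|---|---|---|
| 8 | 8/14 = 57% | 9/13 = 69% | 31-43% |
| 10 | 10/14 = 71% | 11/13 = 85% | 15-29% |
| 12 | 12/14 = 86% | 13/13 = 100% | 0-14% |
| 13 | 13/14 = 93% | 100% | 0-7% |
| 15 | 100% | 100% | 0% |

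For a second trimester of 14 weeks, the share before invitation is max(0, (week + lag - T)/14). At week 12 it is 0. At week 15 it runs from (15 - 14)/14 = 7% to (16 - 13)/14 = 21%. The limited exposure is thus mainly a first-trimester matter. The enrolment distribution is not given, so no average over patients can be stated.

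**2. What the contrast estimates**

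Clinicians were randomized and the analysis follows original assignment, so the arm difference in any trimester compares the package with usual care. Newsletters on discussing weight gain are not limited to any trimester. A first-trimester difference could come from them, and a second- or third-trimester difference mixes them with the app. No trimester isolates the app. Restricting app claims to the later trimesters would therefore not be supported by the design either.

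**3. Precision from adjusting for early gain**

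With m = 1335/58 = 23.0 patients per clinician, the variance of the arm difference is proportional to ICC + (1 - ICC)(1 - r²)/m. Here r is the correlation of the early covariate with the outcome, and the between-clinician part is taken as unreduced.

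Total gain stands in for rate. With e and l the SDs of gain before and after app start, and c their correlation, the squared correlation of gain to app start with total gain is (e + c·l)²/(e² + l² + 2c·e·l).

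- Low case, e = 2, l = 5.5, c = -0.2: 0.81/29.85 = 0.027.
- High case, e = 3, l = 5, c = 0.3: 20.25/43 = 0.471.

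An early clinic weight would capture only part of this. An assumed correlation of 0.6-0.8 with gain to app start multiplies these by 0.36-0.64, giving r² from 0.0098 to 0.301. This step also supposes that the early weight predicts total gain only through gain to app start.

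- Low case, ICC 0.05: (0.05 + 0.95 × 0.9902/23.0)/(0.05 + 0.95/23.0) = 0.0909/0.0913. The standard error falls by about 0.2%.
- High case, ICC 0.01: (0.01 + 0.99 × 0.699/23.0)/(0.01 + 0.99/23.0) = 0.0401/0.0530. The standard error falls by about 13%.
- A middle case set directly at r = 0.3, ICC 0.02: the standard-error ratio is 0.97, equivalent to about 1,422 patients instead of 1,335.

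**The case for a change.** The best case for a change is that the misreading is predictable and cheap to prevent. DATA ANALYSIS frames its target as the effect of the mHealth intervention, and a first-trimester estimate under that label invites the reader to think of the app. Stating the trimester limits and labelling the first as mainly pre-app would cost a few words. A supportive model with early gain would add two covariates (the gain, and gestational age at that weight) and leave the main model intact.

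The timing argument stands: for enrolment from about week 8, most of the first trimester precedes the invitation. The remedy adds little, for these reasons.

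- A trimester-specific analysis already gives each trimester its own estimate. A label changes no estimate, and the text reviewed makes no app-only claim.
- The planned trajectory models use repeated weights and can show when the arms diverge without relying on trimester blocks.
- The supportive model needs a weight taken before enrolment and before any newsletter-prompted counselling. A measured pregravid weight is documented, but dated early prenatal weights are only implied and counselling dates are not mentioned.
- Because clinicians were randomized first, early gain may already reflect the newsletters, and adjusting for it could remove part of the effect.
- The document is written in the past tense, so a covariate added now would be post hoc beside a set declared a priori.

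On recruitment differences, the worry is legitimate in any trial that enrols patients after randomizing clusters. However, both arms received the same survey invitation and the same notice of a possible mHealth program, and no early imbalance is shown.

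**Conclusion.** No change is needed. The trimester contrast is a valid comparison of randomized packages, with limited app exposure in the first trimester: 57-69% of it precedes invitation for enrolment at week 8 and 86-100% at week 12, if the trimester lasts 13-14 weeks and the lag is 0-1 week. That bears on interpretation and introduces no bias. Analysts would reasonably note it when reporting, and would describe results in every trimester as effects of the package.

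Omitting early gain from the rate model is a fair trade-off. The possible saving of about 0.2-13% in standard error rests on assumed SDs, correlations and ICC, and could be negligible. Against it stand a covariate that may post-date randomization and data whose availability is not shown.

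Two limits apply. That a first-trimester estimate will be reported at all is inferred from the term trimester-specific. Trimester limits or outcome definitions may also be given in parts of the document not available for this check.
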